 - Vitals at (Treatment Period 5, Day 0) predose (T-0), intradose after the start of study drug IV infusion (SEL-037) at 15, 30, 45, 60, 90, 120, and 180 minutes, then at 6 hours; and then at Treatment Period 5, Day 1, 7, 14, 21 and 30 or early termination
 - ECG exam at (Treatment Period 5, Day 0) predose and End of Study Treatment Period 5, Day 30 or early termination.
- Part B - Treatment period 5 - Cohort 3 (0.05 mg/kg SEL-110 + 0.2 mg/kg SEL-037), Cohort 4 (0.05 mg/kg SEL-110 + 0.4 mg/kg SEL-037), Cohort 5 (0.08 mg/kg SEL-110 + 0.2 mg/kg SEL-037), Cohort 6 (0.08 mg/kg SEL-110 + 0.4 mg/kg SEL-037), Cohort 7 (0.1 mg/kg SEL-110 + 0.2 mg/kg SEL-037), Cohort 8 (0.1 mg/kg SEL-110 + 0.4 mg/kg SEL-037), Cohort 10 (0.125 mg/kg SEL-110 + 0.4 mg/kg SEL-037), Cohort 11 (0.15 mg/kg SEL-110 + 0.2 mg/kg SEL-037), and Cohort 12 (0.15 mg/kg SEL-110 + 0.4 mg/kg SEL-037)

- Vitals at (Treatment Period 5, Day 0) predose (T-0), intradose after the start of study drug IV infusion (SEL-037) at 15, 30, 45, 60, 90, 120 and 180 minutes, then at 6 hours; and then at Day 1, 7, 14, 21 and 30 or early termination.
- ECG exam at (Treatment Period 5, Day 0) predose and End of Study Treatment Period 5, Day 30 or early termination.
- Adverse events (AE) and serious adverse events (SAE) starting at dosing. AEs will be graded according to Rheumatology Common Toxicity Criteria, version 2.0. If a severe infusion reaction occurs, a determination of anaphylaxis (Grade 4 reaction) will be based on the National Institute of Allergy and Infectious Diseases (NIAID)/ Food Allergy & Anaphylaxis Network (FAAN) Anaphylaxis Criteria.
- Concomitant medication usage will be recorded throughout the trial.
- Clinical laboratory tests (blood chemistry, hematology including clotting parameters, and urinalysis) per the Time and Events Schedule.
- Immunogenicity samples for anti-PEG antibodies at the Screening Visit and for anti-pegsiticase, anti-uricase, and anti-PEG antibodies at baseline (predose for Treatment Periods 1, 2, 3, 4 and 5), Day 7, 14, and 21 post each treatment for Treatment Periods 1, 2, 3, 4, and 5, and EOS / early termination (Treatment Period 5, Day 30).

Safety (Part C, Cohorts 13, 15, and 17):

Note: Cohorts 14 and 16 are intentionally omitted from this protocol in order to maintain the cohort numbering convention of associating odd numbered cohorts with the 0.2 mg/kg SEL-037 dose.

- Physical exam at the Screening Visit and Treatment Period 5, Day 30/early termination.

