7. SELECTION AND WITHDRAWAL OF SUBJECTS

7.1. Subject Inclusion Criteria

1. Has provided written informed consent prior to the conduct of any study specific procedures and continues to provide consent;
2. Understands and is willing and able to comply with study requirements, including the schedule of follow-up visits, and has demonstrated compliance with study requirements during Screening;
3. At the Screening Visit male age 21 - 75, inclusive or female age 21-75 of non-child bearing potential;
4. Has at the Screening Visit a serum uric acid ≥ 6 mg/dL, with established or symptomatic gout which is defined as having at least **ONE** of any of the 3 following factors:
 - a. ≥ 1 tophus
 - b. 1 gout flare within the last 6 months
 - c. Chronic gouty arthropathy
5. The use of allopurinol, febuxostat (Uloric[®]), or probenecid as uric acid-lowering therapy is permissible if dosing has been stable for at least the month prior to the Screening Visit and remains stable during the Screening Phase (i.e., no initiation, change in dose or discontinuation 1 month prior to screening and during screening).
6. Is negative for anti-PEG antibodies at the Screening Visit;
7. Has not participated in a clinical trial within 30 days of the Screening Visit and agrees to not participate in a clinical trial for the duration of the study;
8. Negative serology for HIV-1/-2 and negative antibodies to hepatitis C;
9. Has adequate venous access and able to receive IV therapy;
10. If applicable, has fully recovered from any prior surgery;
11. Is not presently receiving any vaccination scheme or have received a live virus vaccine in the previous 6 months.

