10.2. Analytical Procedures

Serum samples for SEL-037, for uricase activity and for uric acid determinations and whole blood samples for rapamycin determinations will be measured by validated methods. Serum samples for antibody (anti-PEG, anti-uricase, and anti-pegsiticase) determinations will be measured by validated methods. Procedures for processing samples will be included in the Study Manual.

Anti-pegsiticase, anti-uricase and anti-PEG samples will be sampled as per the schedule of events. At minimum, the samples to be analyzed will include the Day 14 and pre-dose samples for each treatment period as well as the Day 7, 14, 21 and EOS/Early Termination visit for the final treatment period for each subject.

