4.4. IMMUNOGENICITY ENDPOINTS

Immunogenicity endpoints include occurrence of anti-PEG, anti-pegsiticase, and anti-uricase specific antibodies based on screening assay; and the titer for the anti-pegsiticase antibodies, where the confirmation assay is also available. Frequency of occurrence of antibodies by study day and overall by cohort, time of onset immunogenicity, and time of resolution of immunogenicity will be calculated and summarized by treatment in summary tables. Time of onset is defined as the first time point with positive ADA (anti-drug antibodies) result; time of resolution is defined as the

1008142

SELECTA Biosciences

SEL - 212/201

SAP Version: Final 2.0

Statistical Analysis Plan

first time point when a previously observed positive ADA result returns to baseline. Titers of antibodies against PEG, uricase and pegsiticase will be listed.

Statistical Analysis Plan

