6.2. KEY DEFINITIONS

The last non-missing value prior to the start of infusion of any study drug in Period 1 will be used as baseline.

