10.3. DATA SUMMARIZATION

Tables summarizing the frequency of the occurrence of ADAs by dose and by time point with overall summary per treatment will be produced for all cohorts separately and combined. The time of onset of immunogenicity, duration and number of resolved ADA cases will be summarized.

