10.4. DATA PRESENTATION FOR IMMUNOGENICITY

Immunogenicity sampling times and results will be listed for safety analysis set outlined in Section 5.2 in this SAP. Immunogenicity endpoints include occurrence of anti-PEG, anti-pegsiticase, and anti-uricase specific antibodies based on screening assay and the titer for the anti-drug antibodies as identified in the confirmation assay.

Frequency of occurrence of antibodies by study day and overall by cohort, time of onset immunogenicity and time of resolution of immunogenicity will be calculated and summarized by treatment in summary tables. Time of onset is defined as 1st time point with positive ADA result; time of resolution is defined as 1st time point when previously observed positive ADA result returns to baseline. Titer of antibodies against PEG, uricase and pegsiticase will be listed. The effect of possible antibody responses on PK and PD parameters will be evaluated descriptively.

Cumulative positive ADA result for subject will be defined for each treatment period separately as at least one positive antibody post-dose time point for each Treatment period and Overall. The ADA positive subjects will be also stratified by the titer values for anti-pegsiticase and anti-uricase. The limits for titer values for low, moderate and high range will be identified based on percentiles after review of actual data (for example ≤ 30 percentile - low, 31-70 percentile - moderate, 71-100 percentile - high). Cumulative negative result will be defined as negative ADA result at all time points for a subject during each Treatment period.

Following tables will be produced to evaluate effect of immunogenicity on PK:

Statistical Analysis Plan

- Descriptive statistics of the key PD parameters based on measured values and $\%CFB$, $\%CFB_{\min}$, $AUE_{\%CFBlast}$, and $TA_AUE_{\%CFBlast}$ as well as uric acid concentration and $\%CFB$ on day 21 of each treatment period for ADA positive and negative, ADA low, moderate and high titer groups including Q1, Q3, 5, 10, 90 and 95 percentiles. The data will be presented by cohort and overall.
- Descriptive statistics of the key PK parameters based on measured values and C_{\max} , T_{\max} , AUC_{0-last} , and AUC_{0-inf} for ADA positive and negative, ADA low, moderate and high titer groups including Q1, Q3, 5, 10, 90 and 95 percentiles. The data will be presented by cohort and overall.

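### ADA resolution is fixed at the first return to baseline whatever follows, so a case that turns positive again still counts as resolved, with a shortened duration

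*SAP*

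**What the plan says.** SAP 4.4 places the time of resolution at the "first time point when a previously observed positive ADA result returns to baseline". SAP 10.4 repeats the rule: "time of resolution is defined as 1st time point when previously observed positive ADA result returns to baseline". Onset is treated in the same first-event way: "Time of onset is defined as 1st time point with positive ADA result". SAP 10.3 then promises the output: "The time of onset of immunogenicity, duration and number of resolved ADA cases will be summarized". Neither a resolved case nor ADA duration is defined separately; the natural reading of duration is onset to resolution. No section says how a case that becomes positive again is counted.

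Baseline comes from SAP 6.2: "The last non-missing value prior to the start of infusion of any study drug in Period 1 will be used as baseline". Entry requires antibody negativity for one specificity only (Protocol 7.1): "Is negative for anti-PEG antibodies at the Screening Visit". A return to baseline is therefore not always a negative result for anti-uricase or anti-pegsiticase.

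For sampling, the Protocol synopsis lists pre-dose samples, "Day 7, 14, and 21 post each treatment for Treatment Periods 1, 2, 3, 4, and 5", and an end-of-study or early-termination sample. Not all need be assayed. Protocol 10.2 says "At minimum, the samples to be analyzed will include the Day 14 and pre-dose samples for each treatment period", plus all visits of the subject's final period. SAP 6.1 lists Early Termination data but keeps them out of summaries.

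**The concern.** A rule that stops at the first return ignores everything after it. Take a subject with results +, -, +, + on Days 7, 14, 21 and 28 of Period 1. Onset is Day 7, resolution is Day 14, duration is 7 days, and the case is resolved, although the antibody is present at the next dose. Subjects are re-exposed to SEL-037 every period, so the SAP needs a rule for such reversals.

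Immunogenicity is a secondary objective, and the product is meant to keep repeated SEL-037 doses effective. A table of resolved cases and short episodes could be read as evidence of tolerance. Follow-up is also unequal and linked to response. Under Protocol 6.3.1, SEL-110 cohort subjects are re-dosed only if Day 21 serum uric acid is at or below 1.0 mg/dL; the others leave about 30 days after their last dose. The number of samples that could trigger the rule therefore differs between subjects.

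**Working it through.** The plan gives no figure for resolved cases, so there is nothing to reproduce. The check has four steps.

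**1. Direction, with no assumed rate.** Every case that meets a sustained definition also has a first return, at the same time or earlier. The first-return count is therefore at least the sustained count, and the onset-to-resolution time is at most the sustained one.

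**2. Number of samples.** Each period has Days 7, 14 and 21 plus the next pre-dose or final visit, which makes 4 post-dose samples.
- Stopped after Period 1: 4 samples, or 3 if the Early Termination visit is left out under SAP 6.1.
- Five periods, all assayed: 5 × 4 = 20, plus one at the Day 60 visit for some (Protocol 10.1.1).
- Five periods, minimum assay set: 4 × 2 + 4 = 12.

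With onset at the first assayed post-dose sample, the samples after onset are k = 3, 19 and 11 respectively (4, 20 and 12, less one).

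**3. A truly persistent antibody.** Let q be the chance that one sample reads as baseline. This is an assumption, taken over 0.02 to 0.20, with independent samples.
- Called resolved: 1 - (1-q)^k
- Called resolved although the last sample is positive: (1-q) × [1 - (1-q)^(k-1)]

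For q = 0.05 and k = 3: 1 - 0.95³ = 14.3%, and 0.95 × (1 - 0.95²) = 9.3%. Each cell gives called resolved / of which last sample positive, as percentages of all such subjects:

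| q | k = 3 | k = 11 | k = 19 |
|---|---|---|---|
| 0.02 | 5.9 / 3.9 | 19.9 / 17.9 | 31.9 / 29.9 |
| 0.05 | 14.3 / 9.3 | 43.1 / 38.1 | 62.3 / 57.3 |
| 0.10 | 27.1 / 17.1 | 68.6 / 58.6 | 86.5 / 76.5 |
| 0.20 | 48.8 / 28.8 | 91.4 / 71.4 | 98.6 / 78.6 |

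**4. Allowing true seroreversion.** Let h be the assumed chance per sample that the antibody truly disappears. With q = 0.05, the percentage called resolved with a positive last sample (simulation, 40,000 subjects per cell) is:

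| h | k = 3 | 7 | 11 | 15 | 19 |
|---|---|---|---|---|---|
| 0.05 | 7.9 | 17.5 | 21.6 | 22.3 | 21.3 |
| 0.10 | 6.8 | 12.0 | 12.2 | 10.0 | 7.8 |
| 0.20 | 4.6 | 5.2 | 3.3 | 1.8 | 0.9 |

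The rise with follow-up in step 3 flattens at h = 0.05 and is lost by h = 0.10. At h = 0.20 the longest follow-up has the smallest over-count.

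**The case against.** The SAP defines a time of resolution, not a resolved case, so an analyst could still count reversals sensibly. That is possible, but nothing directs it, and a subject with a resolution time is most naturally tabulated as resolved.

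A reader might go further and infer that over-counting is greatest in subjects followed longest, so that cohorts with sustained response look more tolerant than they are. The documents do not support this. Neither q nor h is given, and step 4 shows that the gradient can reverse. The 19-sample case needs early onset and every sample assayed, whereas Protocol 10.2 guarantees about 12 post-dose samples. Protocol 4.3.2.1 and 4.3.2.3 link ADA to loss of uric acid control, so many persistent positives may stop early.

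The effect is also contained. SAP 10.5 compares treatments mainly on ADA frequency, together with time of onset, and without inference. Frequency by time point is tabulated and results are listed, so reversals remain visible. A subject with one positive post-dose sample stays in the cumulative positive group. All of this stands and limits the weight of the point, but a listing does not correct a summary table of resolved cases.

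**Conclusion.** The point holds for the definition. As written, the rule gives a resolution time and a shortened duration to cases that are positive again later, and its error against a sustained definition runs one way only. That conclusion needs no assumed rate. The size does: for a persistent antibody at q = 0.05, 14% to 62% would be called resolved as later samples rise from 3 to 19, assuming independent samples and no true seroreversion. These figures are illustrations, not estimates for this trial.

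Opportunity for a spurious return rises with the number of post-onset samples. The size and direction of any difference between cohorts remain open. Only the resolved count, the resolution time and the duration are affected. The change is worth making before the tables are produced, but no planned inference depends on it.

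**What to change.** In SAP 4.4 and 10.4, define a resolved case as a return to baseline status that holds at all later available samples, with at least two samples at that status. Include EOS, Early Termination and Day 60 samples where taken, as a stated exception to SAP 6.1; otherwise a final positive at early termination would drop out. State what baseline status means for a subject who is positive before the first dose.

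Assign the categories in this order:
1. Ongoing: the last available sample is positive.
2. Intermittent: positive again after a return, and not ongoing.
3. Not evaluable for resolution: only one later sample is available to show the return.
4. Resolved: all others.

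Define duration as first to last positive sample, flagged as ongoing where the last is positive. For an uninterrupted episode this is one sampling interval shorter than onset to return, so the table should state its basis. Show the number of post-onset samples beside the resolved count.

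A persistent antibody can then be called resolved only if its last two samples both read as baseline, a chance of at most q²: 0.25% at q = 0.05 and 1% at q = 0.10.

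The cost is SAP wording and one derivation, with no new data collection. Fewer cases will be reported as resolved. An isolated late false positive can also move a truly resolved case to intermittent or ongoing. At an assumed 5% per sample, this affects 1 - 0.95² = 10% of such cases with 2 samples after the return and 1 - 0.95¹⁶ = 56% with 16. The new rule therefore also depends on follow-up, which is a further reason to show the sample counts.

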Mean \pm SD serum concentration-time profiles will be presented on linear and log-linear scales for all Treatment periods within the same figure for each cohort separately. PK concentrations of SEL-037 and uricase activity will be also presented on the same plot with double Y axes for each Cohort and Treatment period separately.

Additionally mean \pm SD serum concentration-time profiles will be presented on linear and log-linear scales for all cohorts in Parts A/B with 0.2 mg/kg SEL-037 (cohorts 1, 3, 5, 7, 11) or 0.4 mg/kg dose levels (cohorts 2, 4, 6, 8, 10, 12) within the same figure for each treatment period separately. Cohorts 13, 15 in Part C of the study will be presented separately.

Individual serum concentration-time profiles will be presented, for each Cohort and Treatment period with all subjects in the same figure on linear and log-linear scales.

Regression/scatter plots for SEL-037 PK parameters (C_{max} , AUC_{0-last} , AUC_{0-inf}) for dose levels 0.2 and 0.4 mg/kg separately versus dose of SEL-110 (for cohorts 1 and 2, the SEL-110 dose level will be set to 0) on the same plot for each parameter individually. The plots will be produced for all treatment periods in Part A of the study separately and can be combined for treatment periods 1-3 with Part C data cohorts 13, 15 as additional plot.

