8.6. ASSESSMENT OF DOSE PROPORTIONALITY FOR SEL-037

Single and multiple dose PK parameters for SEL-037 PK concentrations or uricase activity C_{max} , C_{min} , AUC_{0-last} , AUC_{tau} normalized by dose of SEL-037 will be compared between cohorts 1, 3, 5, 7, 11 with 0.2 mg/kg and 2, 4, 6, 8, 10, 12 with 0.4 mg/kg doses of SEL-037 using ANOVA model separately for Parts A and B and each treatment period and combined data for Parts A and C (treatment periods 1-3 only).

For Part A of each cohort, the dose of SEL-110 will be included as fixed effect in this comparison.

The dose normalized PK parameters for SEL-037 will be presented on box plots for each treatment and part separately and overall for all cohorts with the same dose level for comparison for Parts A and B and separately for combined data Parts A and C (treatment periods 1-3).

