10. ANALYSIS OF IMMUNOGENICITY

Immunogenicity endpoints include screening and confirmation results for IgG antibodies to pegsiticase, uricase, and IgM anti-PEG antibody. The titer for the anti-pegsiticase IgG antibodies will be determined during confirmation assay. The titer for the anti-uricase IgGs will be reported for positive samples. Preliminary concentration for anti-PEG IgM will be estimated in screening assay and confirmed in confirmation assay using multiple dilutions.

The Parts A/B (Treatment periods 1-3 and 4-5 for cohorts 1-8, 10-12 respectively) will be presented together separately from Part C (cohorts 13, 15) unless necessary for comparative analysis.

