- Frequency summary of subjects for ADA positive and negative results on day 21 as well as titer groups stratified by stopping rule from the protocol - subjects who had serum uric acid (sUA) value less than or equal to 1.0 mg/dL at any of the Day 21 visits and were eligible for the next dosing of SEL-212 (or SEL-037) vs subjects who had > 1mg/dL sUA at this time point. The results for the treatment periods will be time-matched between immunogenicity testing and sUA concentration measurement. The data will be presented by cohort and overall.
- Additionally model for the evaluation of the dose effect of SEL-110 and SEL-037 on PD results described in the section 9.6 of the SAP may be repeated with additional covariate for immunogenicity (cumulative positive, negative, positive low, high and moderate titer) to evaluate if immunogenicity had an additive or individual effect on the sUA as compared to the dose effect.

Following plots will be presented for immunogenicity and PK parameters:

Box and whiskers plot for comparison of CL values for SEL-037 (pegsiticase), C_{\max} , T_{\max} , AUC_{0-last} , and AUC_{0-inf} derived using both PK concentrations and uricase activity between subjects with cumulative positive and negative immunogenicity results for each antigen separately (PEG, uricase or pegsiticase) by Cohort with varying doses of SEL-110 and overall. The additional plots will be created for the Part C.

Following plots will be presented for immunogenicity and PD parameters:

Box and whiskers plot for comparison of C_{\min} , CFB_{\min} , $AUE_{CFBlast}$ and $TA_AUE_{CFBlast}$, $\%CFB_{\min}$, $AUE_{\%CFBlast}$ and $TA_AUE_{\%CFBlast}$ values for uric acid between subjects with cumulative positive and negative immunogenicity results for each antigen separately (PEG, uricase or pegsiticase) by cohort and overall.

Statistical Analysis Plan

10.5. ASSESSMENT OF THE EFFECTS OF IMMUNOGENICITY OF PHARMACOKINETICS OF SEL-037(PEGSITICASE) AND ON PD PARAMETERS OF URIC ACID

The effect of possible antibody responses on PK parameters will be evaluated descriptively.

Immunogenicity results will be compared descriptively between treatments using frequency of each type of ADA as main parameter as well as the time of onset of immunogenicity.

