The CL for SEL-037 (pegsiticase), C_{max} , T_{max} , AUC_{0-last} , and AUC_{0-inf} derived using both PK concentrations and uricase activity will be compared between subjects with cumulative negative and cumulative positive ADA results by Treatment period and cohort and overall for each cohort individually in the descriptive statistics table.

Similarly, PD parameters C_{min} , CFB_{min} , $AUE_{CFBlast}$, $TA_AUE_{CFBlast}$, $\%CFB_{min}$, $AUE_{\%CFBlast}$ and $TA_AUE_{\%CFBlast}$ will be compared between subjects with cumulative negative and cumulative positive ADA results by Treatment period and cohort and overall for each cohort individually in the descriptive statistics table.

No statistical inferences will be done for the comparisons.

Statistical Analysis Plan

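### In SAP 10.4, the overall ADA comparisons of measured SEL-037 Cmax and AUC pool the 0.2 and 0.4 mg/kg cohorts, so any dose imbalance between ADA groups enters the apparent antibody effect

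*SAP*

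**What the plan says.** SAP 10.4 plans a table giving "Descriptive statistics of the key PK parameters based on measured values and" naming Cmax, Tmax, AUC0-last and AUC0-inf. Its columns are ADA-positive and ADA-negative subjects and the low, moderate and high titer groups. It includes quartiles and the 5th, 10th, 90th and 95th percentiles. On grouping it says: "The data will be presented by cohort and overall". Box plots of CL, Cmax, Tmax and the two AUCs compare cumulative ADA-positive with cumulative ADA-negative subjects "for each antigen separately (PEG, uricase or pegsiticase) by Cohort with varying doses of SEL-110 and overall". The PK box plots are not split by titer.

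Section 10 opens by stating that Parts A/B "will be presented together separately from Part C". Parts A/B contain both SEL-037 dose levels, which SAP 8.4 lists as "0.2 mg/kg SEL-037 (cohorts 1, 3, 5, 7, 11) or 0.4 mg/kg dose levels (cohorts 2, 4, 6, 8, 10, 12"). Part C uses 0.2 mg/kg throughout.

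Elsewhere the SAP keeps the two doses apart. In 8.6, SEL-037 Cmax, Cmin, AUC0-last and AUCtau "normalized by dose of SEL-037 will be compared between cohorts 1, 3, 5, 7, 11 with 0.2 mg/kg" and the 0.4 mg/kg cohorts. Section 8.7 models the effect of SEL-110 on SEL-037 exposure separately at each SEL-037 dose. The general normalisation rule in 8.2 covers SEL-110 parameters only. Section 10 contains no corresponding step.

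**The concern.** Measured Cmax and AUC depend on dose as well as on antibodies. When cohorts given 0.2 mg/kg are pooled with cohorts given 0.4 mg/kg, the ADA-positive versus ADA-negative contrast carries a dose component unless both ADA groups happen to have the same dose mix. That component can imitate an antibody effect on exposure, or hide one.

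PK and immunogenicity of SEL-037 are secondary objectives, and these displays are how the SAP describes the link between them. Each cohort is planned at 6-20 subjects. Once split by ADA status and then by titer, the by-cohort cells are small, which makes the overall rows an attractive summary.

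**Working it through.** The plan gives no sample size, power or expected effect for this comparison, so there is no planned figure to reproduce.

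**Inputs from the documents**
- SEL-037 doses in Parts A/B: 0.2 mg/kg in five cohorts and 0.4 mg/kg in six. Dose ratio 0.4/0.2 = 2.
- About 100 subjects in 11 cohorts of 6-20.
- SEL-110 doses (mg/kg) at 0.2 mg/kg SEL-037: 0, 0.05, 0.08, 0.1, 0.15. The 0.4 mg/kg cohorts have the same levels plus 0.125 (Cohort 10).

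**Assumptions (not in the documents)**
- Exposure is proportional to SEL-037 dose.
- ADA rates by SEL-037 dose lie between 40% and 80%.
- Within-dose geometric CV is 30% to 50%.

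**1. Shift in the pooled ratio.** Let f_pos and f_neg be the shares of ADA-positive and ADA-negative subjects who received 0.4 mg/kg. With no antibody effect at all, the pooled ratio of geometric means (positive/negative) is 2^(f_pos − f_neg).

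| Difference in share | Factor |
|---|---|
| 10 points | 2^0.1 = 1.07 |
| 20 points | 2^0.2 = 1.15 |
| 30 points | 2^0.3 = 1.23 |

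**2. If ADA rates differ by SEL-037 dose (assumed rates, 50 subjects per dose).**
- 60% at 0.2 and 40% at 0.4 mg/kg: f_pos = 20/50 = 0.40, f_neg = 30/50 = 0.60, ratio 2^(−0.20) = 0.87.
- 40% and 60%: ratio 2^(0.20) = 1.15.
- 80% and 40%: f_pos = 20/60 = 0.33, f_neg = 30/40 = 0.75, ratio 0.75.
- Equal rates: ratio 1.00.

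A true antibody ratio of 0.70 would read as 0.70 × 0.87 = 0.61 or 0.70 × 1.15 = 0.80 when the shares differ by 20 points in either direction.

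**3. If ADA depends only on SEL-110 dose.** For illustration, assume equal cohort sizes and an ADA rate falling linearly from 80% at no SEL-110 to 40% at 0.15 mg/kg. In units of one cohort:
- ADA-positive: 2.99 at 0.2 and 3.45 at 0.4 mg/kg, so f_pos = 3.45/6.44 = 0.536.
- ADA-negative: 2.01 and 2.55, so f_neg = 2.55/4.56 = 0.558.
- Ratio 2^(−0.022) = 0.985, a shift of about 1.5%.

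The near-balance arises because every SEL-110 level except 0.125 is paired across the two SEL-037 doses. Unequal cohort sizes can enlarge the shift to a few percent.

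**4. Added spread, whatever the ADA rates.** With share p at 0.4 mg/kg, pooling adds a log-SD of ln 2 × √(p(1 − p)). This is 0.35 at p = 0.5 and 0.34 at p = 0.62. At p = 0.5 the added variance is 0.120:
- CV 30%: √(exp(0.086 + 0.120) − 1) = 48%.
- CV 50%: √(exp(0.223 + 0.120) − 1) = 64%.

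**5. After the change.** Within one SEL-037 dose level the dose factor is 1 by construction. After division by dose it is 2^0 = 1 under proportionality.

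**The case against.** *The word overall is not defined in 10.4, and elsewhere in Section 10 it sometimes means across time points.* True, and a definition would help. But when the SAP means within a cohort it says so: the 10.5 comparison is made "by Treatment period and cohort and overall for each cohort individually in the descriptive statistics table". Pooling across cohorts is the plain reading of the 10.4 wording, "by Cohort with varying doses of SEL-110 and overall".

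*A dose-adjusted comparison is already planned.* This largely stands for total exposure. CL is dose/AUCinf (SAP 8.2) and is in the overall box plots, and dose-normalised AUC0-inf is in effect its reciprocal. CL is not in the 10.4 table, however, and says nothing about Cmax or AUC0-last. Under 8.2 it is also dropped from summaries when the terminal slope is unreliable or extrapolation exceeds 20%.

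*The documented driver of antibody formation is SEL-110 dose, which is nearly balanced across SEL-037 doses.* This stands, and it is why the shift may be small. The Phase 1 study of SEL-037 alone (Protocol 4.3.2.1) shows no clear trend with SEL-037 dose: ADA with reduced activity at Day 14 in 3, 2, 3 and 2 subjects at 0.1, 0.2, 0.4 and 0.8 mg/kg, group sizes not given.

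*Two-fold exposure presumes dose proportionality, which 8.6 is there to examine.* This also stands, and it favours showing the doses separately over dividing by dose.

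*The comparisons are descriptive.* Correct. SAP 10.5 rules out inference, so no test or interval is invalidated.

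**Conclusion.** The point holds for two displays in SAP 10.4: the overall rows of the ADA-by-PK table and the overall ADA-positive versus ADA-negative box plots of Cmax, AUC0-last and AUC0-inf in Parts A/B. Under approximate dose proportionality, each 10 points of imbalance in the 0.4 mg/kg share moves the apparent antibody effect by about 7%. The added log-SD of about 0.34 does not depend on ADA rates.

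Three stronger readings are tempting and are not supported:
- A reader might infer a known, sizeable bias of 12-15% or more in a given direction. That needs ADA rates to differ by SEL-037 dose, and the documents give no such rates.
- A reader might infer that all of Section 10 is affected. By-cohort displays and 10.5 hold dose fixed, CL already allows for dose, and Part C has a single SEL-037 dose.
- A reader might treat the wider spread as lost sample size. With no test or interval planned, it only blurs the descriptive percentiles and plots.

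Severity is modest: unconfounded results will exist alongside the mixed ones. The change is worth making because it costs little and brings 10.4 into line with 8.6 and 8.7.

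**What to change.** In SAP 10.4 only:
1. Define overall as pooled across cohorts.
2. Show the overall Cmax, AUC0-last and AUC0-inf rows and box plots separately for 0.2 and 0.4 mg/kg SEL-037. This is preferable because it does not rely on dose proportionality. Alternatively, show them divided by SEL-037 dose.
3. Add CL to the ADA-by-PK table.

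Leave the by-cohort rows, the CL plots, Section 10.5 and the Part C displays as they are.

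The cost is a sentence or two of SAP text and minor programming, with no new data. Dose-normalised Cmax and AUC0-last are already derived for 8.6. AUC0-inf is not on that list and would need one extra division if normalisation is chosen.
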